4.2. Purpose

The purpose of the study is to evaluate the safety and efficacy of the Advanced Hybrid Closed Loop (AHCL) in comparison with sub-optimally controlled patients on Multiple Daily Injection (MDI) therapy with Flash Glucose Monitoring (FGM) or Real-Time Continuous Glucose Monitoring (CGM) over 6 months duration.

5. Objective and Endpoints

5.1. Primary Objective

The primary objective of the study is to evaluate the superiority on glycemic control of the AHCL system versus MDI + FGM with patients with Type 1 Diabetes.

5.2. Exploratory Objective

A second objective of the study is to conduct an exploratory analysis on the efficacy of the AHCL system versus MDI + RT-CGM with patients with Type 1 Diabetes.

5.3. Endpoints

5.3.1. Primary Endpoint

HbA1c remains the reference marker for assessing glycemic control and predicting the risk of development of long-term complications (Danne, 2017; ICHOM, 2019).

Confirmatory test for the difference in the mean HbA1c change (baseline versus 6 months) between the AHCL and the MDI + FGM arm will be performed.

Measurements will be done from venous blood and analyzed as per National Glycohemoglobin Standardization Program (NGSP) standards in a central laboratory.

5.3.2. Secondary Endpoints

Secondary endpoints include diabetes control parameters to be evaluated in clinical studies following the recommendations from the International Consensus on CGM (Danne, 2017) and the International Consortium for Health Outcomes Measurement (ICHOM) standards for Diabetes (ICHOM, 2019).

Glycemic variability such as Time in Range(s) is now accepted as a clinically valuable marker of glycemic control beyond HbA1c alone (Danne, 2017).

Below secondary endpoints will be assessed in AHCL vs MDI + FGM (Cohort A)

- % Time spent in hyperglycemic range with SG > 250 mg/dL (13.9 mmol/L)
- % Time spent in hyperglycemic range with SG > 180 mg/dL (> 10.0 mmol/L)
- % Time spent within range with sensor glucose (SG) between 70 - 180 mg/dL (3.9-10.0 mmol/L)
- % Time spent in hypoglycemic range with SG < 54 mg/dL (3.0 mmol/L)
- % Time spent in hypoglycemic range with SG < 70 mg/dL (3.9 mmol/L)

5.3.2.1. Safety Endpoint

- Number of severe hypoglycemic events
- Number of DKA events
- Number of Serious Adverse Events (SAE)
- Number of Serious Adverse Device Effects (SADE)
- Number of Unanticipated Serious Adverse Device Effects (USADE)
- Number of Device deficiencies

The above endpoints will also be assessed in Cohort B in an exploratory manner, as well as the difference in the mean HbA1c change (6 months - baseline) between the AHCL and the MDI + RT-CGM arms.

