Risks with Insulin Pump Infusion	Prevention and Mitigation

General risks related to insulin pump infusion set may include:
 
• Localized infection• Skin irritation or redness• Bruising• Discomfort or pain• Bleeding• Irritation• Rash• Occlusions that can interrupt insulin delivery and lead to hyperglycemia or diabetic ketoacidosis	
Prevention and mitigation include:
 
• Patients should be instructed to follow the provided user guides for insertions and care of infusion sets.• If an infusion site becomes irritated or inflamed, the infusion set should be removed and another placed in a new location.• Patients will receive training prior to study on device use and diabetes management principles and will be instructed to call with problems.• Subjects are instructed to check their meter glucose if their high or low symptoms do not match their sensor alerts or sensor glucose readings in order to make diabetes treatment decisions.• Subjects are instructed to check their meter glucose if there are any concerns that the sensor glucose value is not accurate.• Subjects are instructed to have glucose on hand for hypoglycemia.• Change infusion set if suspected catheter occlusion or administer insulin with pen/syringe for persistent hyperglycemia especially if ketones develop.

Risks with hypoglycemia may include: 
• Seizure• Coma• Altered mental status• Loss of consciousness• Cardiovascular event• Death• Risk of rebound hyperglycemia with ketosis	Prevention and mitigation include: 
• Follow the provided user guides for insulin pump management.• Patients will receive training prior to study on device use and diabetes management principles.• Subjects are instructed to check their meter glucose if their low symptoms do not match their sensor alerts or sensor glucose readings in order to make diabetes treatment decisions.• Subjects are instructed to check their meter glucose if there are any concerns that the sensor glucose value is not accurate.• Subjects are instructed if there are no sensor values, no treatment decisions should be made until a BG is confirmed.• Subjects are instructed to have glucose on hand for hypoglycemia.

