11.2. Definitions and Classification

Medtronic uses the definitions provided in ISO 14155:2020 for AE definitions.

Where the definition indicates "device", it refers to any device used in the study. This might be the device under investigation, or any market released component of the system. Medtronic follows MEDDEV 2.7/3 revision 3 (or subsequent versions) guidelines for classifying causality levels; but will apply these causality definitions across all events, not only serious adverse events and definitions have been adapted accordingly.

Severe Hypoglycemia is an event requiring assistance of another person due to altered consciousness to actively administer carbohydrate, glucagon, or other resuscitative actions. This means that the subject was impaired cognitively to the point that he/she was unable to treat his or her self, was unable to verbalize his or her needs, and was incoherent, disoriented and/or combative.

These episodes may be associated with sufficient neuroglycopenia to induce seizure or coma. Plasma glucose measurements may not be available during such an event, but neurological recovery attributable to the restoration of plasma glucose to normal is considered sufficient evidence that the event was induced by a low plasma glucose concentration. (*Adapted from American Diabetes Association Workgroup on Hypoglycemia, Diabetes Care 28:1245-1249, 2005*)

Severe Hyperglycemia is defined as hyperglycemia (blood glucose greater than >300 mg/dL (16.7 mmol/L) with blood glucose ketones greater than > 0.6 mmol/L or accompanied by symptoms of nausea, vomiting or abdominal pain.

Diabetic Ketoacidosis/DKA diagnostic criteria: blood glucose greater than > 250 mg/dL (or greater than > 13.9 mmol/L), arterial pH less than < 7.3 , bicarbonate less than < 15 mEq/L, moderate ketonuria or ketonemia and requiring treatment within a health care facility. (*American Diabetes Association-Diabetes Care, Volume 27, Supplement 1, January 2004; S94-S102*)

Hyperglycemic events will be recorded as DKA if the event includes the presence of all of the following:

- Arterial blood pH less than < 7.30 or serum bicarbonate less than < 15 mEq/L
- Blood glucose greater than > 250 mg/dL (or greater than > 13.9 mmol/L)
- Serum ketones or large/moderate urine ketones
- Symptoms such as polyuria, polydipsia, nausea, or vomiting
- Treatment provided in a health care facility

Adverse Event (AE): (ISO 14155:2020, 3.2)

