11.3.1. Reporting of Adverse Events

The investigator or designee will record all AEs while the subject is enrolled in the clinical study (including at minimum the following information: date of the adverse event, date of first awareness by investigator, action taken, outcome status and resolution, and assessment of both the seriousness and the relationship to the investigational device and procedure).

Each AE needs to be assessed for its device or procedure relatedness. A device related AE is associated with the use of the study device (e.g. infection of sensor site or infusion set occlusion resulting in DKA). A procedure related AE is associated with testing related to the study procedures specified in the CIP.

Examples of device or procedure related AEs include:

- **Device** related: insertion site infection
- Serious adverse **device effect**: cellulitis at device insertion site requiring hospitalization
- **Procedure** related AE: bruising at IV insertion site

Adverse events that have not resolved at the time of the subject's discontinuation or completion of the study should have an "outcome" of Not Recovered/Not Resolved at study end in subject source and on an eCRF. The investigator should ensure that subject is aware of any follow-up or additional treatment that is required for any ongoing AE at end of study participation; however, there will be no eCRF entry for the ongoing follow-up.

Subjects participating in the study have diabetes and are expected to experience hypoglycemia and/or hyperglycemia. These normal events are not expected to be reported to sponsor on an AE eCRF as this is not considered an untoward event, but rather an expected occurrence. Any glycemic excursion that meets the protocol definition of Severe Hypoglycemia, Severe Hyperglycemia or DKA is considered an untoward event and a worsening from the subject's baseline and would be reported to sponsor on an AE eCRF.

Medical conditions should only be reported to sponsor on an AE eCRF, if there is a worsening from the subject's baseline. For example, a subject previously diagnosed with Asthma is hospitalized for severe asthma attack would be a reportable event.

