- In order to establish the relatedness, not all the criteria listed above might be met at the same time, depending on the type of device/procedures and the event.

Example: A severe hyperglycemia AE with the following event description would have the following causality assessment for device relatedness:

Improved glucose without an infusion set/site change	Not related
Changed infusion set with glucose improvement	Possible
Infusion set fell out, bent cannula, occlusion alarm	Causal relationship

12. Data Review Committees

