7.10.2 Number of diabetic ketoacidosis events

A diabetic ketoacidosis event is defined as an event of blood glucose greater than 250 mg/dL(13.9 mmol/L) arterial pH less than 7.3, bicarbonate less than 15mEq/l, moderate ketonuria or ketonemia, and requiring treatment within a health care facility.

Total number of diabetic ketoacidosis events will be reported continuation phase categorized by study arm. The number of diabetic ketoacidosis events per 100 patients' year during the study phase will be calculated in a similar way as in section 7.10.1 and will be reported by periods.

7.10.3 Number of Serious Adverse Events, Serious Adverse Device Effects, Unanticipated Serious Adverse Device Effects and Device Deficiencies

Serious Adverse Event (SAE) is adverse event that led to any of the following:

- a) death,
- b) serious deterioration in the health of the subject, users or other persons as defined by one or more of the following:
 - 1. a life-threatening illness or injury, or
 - 2. a permanent impairment of a body structure or a body function, including chronic disease, or
 - 3. in-patient or prolonged hospitalization, or
 - 4. medical or surgical intervention to prevent life-threatening illness or injury or permanent impairment to a body structure or a body function,
- c) fetal distress, fetal death or a congenital abnormality or birth defect including physical or mental impairment.

NOTE 1: Planned hospitalization for a pre-existing condition, or a procedure required by the CIP, without serious deterioration in health, is not considered a serious adverse event.

For the purpose of this study, the term "life-threatening" in the definition of "serious" refers to an event in which the patient was at risk of death at the time of the event; it does not refer to an event which hypothetically might have caused death if it were more severe.

Serious Adverse Device Effect (SADE) is adverse device effect that has resulted in any of the consequences characteristic of a serious adverse event. Unanticipated Serious Adverse Device Effect (USADE) is serious adverse device effect which by its nature, incidence, severity or outcome has not been identified in the current risk assessment.

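### Severe hyperglycaemia is defined, reportable and the protocol's own example of a device-caused event, but it has no named safety endpoint, count or rate

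*Protocol*

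**What the plan says.** Protocol 11.2 gives severe hyperglycaemia its own definition: "Severe Hyperglycemia is defined as hyperglycemia (blood glucose greater than >300 mg/dL (16.7 mmol/L", together with blood ketones above 0.6 mmol/L or with nausea, vomiting or abdominal pain. Section 11.3.1 exempts ordinary highs and lows from reporting, but not this event: "Any glycemic excursion that meets the protocol definition of Severe Hypoglycemia, Severe Hyperglycemia or DKA is considered an untoward event", to be entered on an adverse event eCRF.

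The protocol also ties the event to the pump. The risk table in 10.1.1 lists "Occlusions that can interrupt insulin delivery and lead to hyperglycemia or diabetic ketoacidosis". Section 11.5 chooses it as the worked example of causality: "A severe hyperglycemia AE with the following event description would have the following causality assessment for device relatedness". A dislodged set, bent cannula or occlusion alarm is there rated a causal relationship.

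The safety endpoints in 5.3.2.1 are severe hypoglycaemia, DKA ("Number of DKA events"), SAEs, SADEs, USADEs and device deficiencies. SAP 7.10 follows the same list: 7.10.1 and 7.10.2 give severe hypoglycaemia and DKA a count and a rate ("Total number of diabetic ketoacidosis events will be reported"), and 7.10.3 counts the serious events and deficiencies. Severe hyperglycaemia is in neither list, nor among the events for the clinical events committee in Protocol 12.1. No reason is given.

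**The concern.** Three events are defined side by side and reported under one rule, and one of them then drops out of the planned summaries. Protocol 13.6 promises descriptive statistics for all secondary, safety and ancillary endpoints, and an event on none of those lists is outside that promise.

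The omitted event is one that the device can cause by a route closed to the comparator: in the study phase AHCL subjects depend on an infusion set while controls inject. Evaluating the safety of AHCL is part of the stated purpose (Protocol 4.2). A ketotic episode after a set failure, recognised and treated at home, would be recorded on the eCRF but would have no planned count or rate by name.

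**Working it through.** **1. Exposure.** Protocol 13.3 assumes SD 0.7, difference 0.5, two-sided alpha 0.05 and 80% power. The normal formula gives 2 × (1.960 + 0.842)² × 0.7² / 0.5² = 30.8, so 31 per arm. The t-based calculation gives 32 per arm (power 80.3%), which is the plan's 64. With 70 randomized 1:1, each arm has 35 subjects, and 35 × 0.5 years = 17.5 patient-years at most, before dropout.

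**2. What zero DKA would show.** The upper limit for a Poisson rate with no events is −ln(0.05) / exposure one-sided, or −ln(0.025) / exposure two-sided.
- Cohort A AHCL arm, randomized phase: 2.996 / 17.5 = 17.1 per 100 patient-years one-sided; 3.689 / 17.5 = 21.1 two-sided.
- All planned Cohort A AHCL exposure, continuation included: 35 × 1.0 + 35 × 0.5 = 52.5 patient-years, limit 5.7 one-sided.
- Both cohorts (35 + 17 = 52 per arm): 52 × 1.5 = 78 patient-years, limit 3.8 one-sided.

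Only the first has a concurrent randomized control.

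**3. DKA as a comparison.** The documents give no DKA rate, so these control rates are assumptions. The test is an exact conditional comparison of two Poisson rates, two-sided 0.05, with 17.5 patient-years per arm.

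| Assumed control rate per 100 patient-years | Expected control events | Chance of no DKA in either arm (equal rates) | Power if the AHCL rate is tripled |
|---|---|---|---|
| 1 | 0.18 | 70% | <0.1% |
| 2 | 0.35 | 50% | 0.1% |
| 5 | 0.88 | 17% | 2.3% |
| 10 | 1.75 | 3% | 13.6% |

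**4. What the added line could show.** At assumed control rates of severe hyperglycaemia of 20, 50 and 100 per 100 patient-years, power is 11%, 32% and 64% for a doubled rate, and 37%, 82% and 99% for a tripled one. The line tells more than DKA only if the event is much more frequent, which the documents do not quantify.

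**5. Whether another planned measure already isolates the event.**
- DKA (Protocol 11.2) requires treatment in a health care facility. An episode managed at home does not qualify.
- SAE and SADE counts take only episodes that meet a seriousness criterion.
- The Device Deficiency eCRF is for deficiencies that did not lead to an adverse event (11.3.2). A set failure that caused the episode is not recorded there.
- Sensor time above 250 mg/dL (secondary) and 350 mg/dL (ancillary) carries neither ketones nor symptoms. In the control arm it comes from two 2-week windows. One 6-hour episode in four weeks is 6 / 672 = 0.9 percentage points.
- Diabetes-related hospital, ICU, emergency and ambulance endpoints (5.3.3) require contact with acute care. SAP 7.11 marks health outcomes as not applicable.
- SAP 7.1.3.3 reports any adverse event in the continuation phase by randomized arm, but specifies no line or rate for this one.

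**The case against.** The best reply is that the gap is narrow. A reader might infer that DKA is all that remains on the hyperglycaemic side, or that a non-serious episode enters no comparison between arms. The documents support neither. Serious episodes are counted as SAEs or SADEs, and the German SAE definition in 11.2 reaches further, to events that could have led to serious deterioration. Time above 250 mg/dL is the first secondary endpoint tested. Acute-care use is classified by diagnosis. SAP 7.1.3.3 reports adverse events by arm, and the data monitoring committee monitors them.

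The SAP supplied covers only the continuation phase, when both arms use AHCL. It cannot show how adverse events would be tabulated for the randomized comparison. Its silence still matters for its own period comparison, which for controls sets injections against AHCL in the same people, and 5.3.2.1 governs the whole trial.

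A reader might also take it as documented that severe hyperglycaemia is the more frequent event, or the harm most likely to differ. Its criteria are less demanding than those of DKA, but no rate is given for either. Protocol 10.3 says only that SAEs were rare in past studies.

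Finally, counts could be uneven for reasons other than the device. The trial is open-label. Section 9.3 schedules 11 study-phase contacts from pump start to Visit 9 in the AHCL arm, against 7 in the control arm. The supply lists show no ketone meter or ketone strips, and controls hand back the study meter at Visits 4, 7B and 9. DKA, which needs facility treatment, is less exposed to this. The point stands, and it limits interpretation, but it is not a reason to leave the event uncounted.

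**Conclusion.** The point holds as a reporting gap: a defined, mandatorily reported and device-linked event has no named endpoint, count or rate, and no other planned measure isolates its non-serious form. DKA is the only named acute hyperglycaemic event. In the randomized Cohort A window, even zero DKA in the AHCL arm is compatible with a rate up to about 17 per 100 patient-years (one-sided 95%, full 17.5 patient-years). That bound concerns DKA in that window only. It does not measure severe hyperglycaemia, and it falls to 5.7 when all planned Cohort A AHCL exposure is counted. The power figures rest on assumed rates.

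It would go too far to conclude that the trial fails its safety objective. Protocol 13.6 makes any safety tests exploratory, with no significance claimed, so what is missing is a descriptive estimate and not a powered test. This is a worthwhile, inexpensive improvement.

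**What to change.** Add the number of severe hyperglycaemia events, by the 11.2 definition, to Protocol 5.3.2.1, and add a matching subsection to SAP 7.10. Report by arm in the study phase and by period in the continuation phase, split by device relatedness: number of events, subjects affected, and events per 100 patient-years (the rate form of SAP 7.10.1) with a confidence interval. Put the same line in whatever analysis plan governs the study phase. State beside the table that the figures are descriptive and that contact frequency and ketone testing may differ between arms.

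The cost is one protocol bullet and one SAP table. Protocol 11.3.1 already requires the event and its relatedness to be recorded, so no visit, procedure or sample-size change is needed, provided that the eCRF allows these events to be identified (the form was not available). Adding the line before analysis also matters because SAP 7.12 would otherwise label it as not pre-specified.

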5.3.3. Ancillary endpoints

- % Time spent in 70 - 140 mg/dL (3.9 -7.8 mmol/L) range
- Area Under the Curve (AUC) in hypoglycemic range with SG < 54 mg/dL (3.0 mmol/L), <70 mg/dL (3.9 mmol/L)
- % Time spent and AUC in hyperglycemic range with SG > 140 mg/dL (7.8 mmol/L), >350 mg/dL (19.4 mmol/L) and AUC in hyperglycemic range with SG >180 (10 mmol/L)), >250 mg/dL (13.9 mmol/L)
- Number of biochemical hypoglycemic events with SG < 54 mg/dL (3.0 mmol/L), < 70 mg/dL (3.9 mmol/L) (defined as sensor values below the threshold per 15 and 20 consecutive minutes).
- Mean of SG values (mg/dL)
- % Time spent in Auto Mode and in Manual Mode

All the above endpoints will be categorized by daytime (06:01 to 23:59) and night-time (00:00 to 06:00) and overall (24h).

- % Time spent in hyperglycemic range with SG > 250 mg/dL (13.9 mmol/L)
- % Time spent in hyperglycemic range with SG > 180 mg/dL (> 10.0 mmol/L)
- % Time spent within range with sensor glucose (SG) between 70 - 180 mg/dL (3.9-10.0 mmol/L)
- % Time spent in hypoglycemic range with SG < 54 mg/dL (3.0 mmol/L)
- % Time spent in hypoglycemic range with SG < 70 mg/dL (3.9 mmol/L)

The above five endpoints will be categorized by daytime (06:01 to 23:59) and night-time (00:00 to 06:00).

- Number of scans and % of sensor readings for MDI + FGM control arm
- % of sensor readings for MDI + RT-CGM control arm only.
- Number of SMBGs in the AHCL arm
- Percentage of sensor use
- Excursion amplitudes of the glucose values measured by mean amplitude of glycemic excursions (MAGE).
- Coefficient of variation of SG values
- Change in Total Daily Dose (TDD) of insulin from baseline to end of study (EOS)
- Change in weight from baseline to EOS
- Change in BMI from baseline to EOS
- Mean HbA1c change (from baseline to 12 months)
- Mean HbA1c change (baseline to 6 month) by age groups and duration of diabetes
- Diabetes-related number and mean duration of hospitalizations, number and mean duration intensive care unit (ICU) care, number of emergency room admissions, number of events requiring ambulance assistance, categorized by reason of diagnosis
- Number of lost days from school or work.
- Hypoglycemia Fear Survey (HFS) score

[figure not shown]
- Diabetes Treatment Satisfaction Questionnaire score
- Diabetes Quality of Life (DQoL) questionnaire score

These ancillary endpoints will also be assessed in Cohort B in an exploratory manner.

6. Study Design

This study is a pre-market, multi-center, prospective, open label, adaptative, confirmatory, randomized controlled trial in insulin-requiring adult subjects with type 1 diabetes on MDI therapy. The study period for each subject will be approximately 13 months.

Figure 3: Study Design

The study consists of two separate cohorts, Cohort A with subjects on MDI + FGM (confirmatory part of the study) and Cohort B with Subjects on MDI + Real-Time CGM (exploratory part of the study). Each cohort will have a separate randomization.

6.1. Duration

Overall study duration from first subject enrollment until the last subject exit is expected to last approximatively 25 months, including an estimated 6-month site activation period, 6-month enrollment period, and a 13-month follow-up period for each subject.

Each subject will enter a run-in phase of approximately 2 weeks, followed by a study phase of 6 months, then a 6-month continuation phase.

